7.7. Concomitant Medications or Therapies

Concomitant medications and therapies, including medications that are taken on an as needed basis and occasional therapies, will be monitored during the study. All concomitant medications will be coded using the WHO drug.

The incidence of concomitant medications and therapies will be summarized using descriptive statistics by therapeutic class category and PT. Patients are counted only once in each therapeutic class, and only once in each PT category. Concomitant medications and therapies will include all medications taken and therapies administered from the first day of study drug administration up to the end of study as defined in the study protocol.

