3.9. Duration of Patient Participation and Justification

This study will consist of an up to 2-week screening period, an open-label treatment period of 104 weeks and an end-of-study visit (at week 106). Patients are expected to participate in this study for its entire duration. See Section 12.4 for the definition of the end of the study.

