5.3. Prior and Concomitant Therapy or Medication

Any prior or concomitant therapy, medication, or procedure a patient has had within 2 weeks prior to screening and up to the end of the study period will be recorded on the CRF. Generic or

trade name, indication, and dosage will be recorded. The sponsor will encode all therapy and medication according to the World Health Organization (WHO) drug dictionary (WHO Drug).

Medications that are not prohibited during the study (see Section 5.3.1) are allowed at the discretion of the investigator and will be documented in the CRF. To the extent possible, patients should continue on medications already prescribed at enrollment; dose modifications and introduction of new medications should be avoided unless deemed necessary for optimal patient care by the investigator.

Disallowed CYP2D6 substrates can be administered only 1 week after the discontinuation of pridopidine (i.e., 1-week washout), to allow enzyme recovery. CYP2D6 inhibitors can be administered to study patients. The concomitant use of medications that are known to have a profound effect on QT interval should be avoided according to the list of permitted and prohibited concomitant medications. [REDACTED]

[REDACTED] concomitant treatment with tetrabenazine is disallowed. Medications that are CYP2D6 substrates and have the potential to reduce the seizure threshold will not be permitted during the study.

Any changes to an existing concomitant medication or any new medication started during the study should be recorded in the CRF. For any concomitant therapy given as a treatment for a new condition or a worsening of an existing condition, the condition must be documented on the AE Form of the CRF.

If a patient receives a prohibited treatment during the randomized phase of the study, he/she will be encouraged to continue in the study and complete the study visits in accordance with the study visit schedule; however, the patient may need to be withdrawn from study treatment (see Section 4.4). If the patient refuses to be seen for further visits, the assessments for End-of-Study (EoS)/Early Termination should be performed, as far as possible (at least attempts to capture information on AEs and concomitant medication).

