9.7.2. Safety Analysis

All adverse events will be coded using the Medical Dictionary for Regulatory Activities (MedDRA). Each patient will be counted only once in each preferred term or SOC category for the analyses of safety. Summaries will be presented for all adverse events (overall and by severity), adverse events determined by the investigator to be related to study treatment (i.e., reasonable possibility; see Section 7.1.4) (defined as related or with missing relationship) (overall and by severity), SAEs, and adverse events causing withdrawal from the study. Summaries will be presented by treatment group and for all patients. Patient listings of SAEs and adverse events leading to withdrawal will be presented.

Changes in laboratory and vital signs measurement data will be summarized descriptively. All values will be compared with prespecified boundaries to identify potentially clinically significant changes or values, and such values will be listed.

The use of concomitant medications will be summarized by therapeutic class using descriptive statistics. Concomitant medications will include all medications taken while the patient is treated with study drug.

For continuous variables, descriptive statistics (n, mean, SD, median, minimum, and maximum) will be provided for actual values and changes from baseline to each time point. For categorical variables, patient counts and percentages will be provided. Descriptive summaries of SAEs, patient withdrawals due to adverse events, and potentially clinically significant abnormal values (clinical laboratory or vital signs) based on predefined criteria will also be provided.

If any patient dies during the study, a listing of deaths will be provided and all relevant information will be discussed in the patient narrative included in the clinical study report.

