The reader of this SAP is encouraged to read the study protocol for details on the conduct of this study, the operational aspects of clinical assessments, and the timing for completing the participation of a patient in this study.

The SAP is intended to be in agreement with the protocol, especially with regards to the primary and all secondary endpoints and their respective analyses. However, the SAP may contain more details regarding these particular points of interest, or other types of analyses (eg other endpoints). When differences exist in descriptions or explanations provided in the study protocol and this SAP, the SAP prevails; the differences will be explained in the Clinical Study Report.

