All patients will be treated with study drug during the course of the study. After the 1 week titration period, patients will be seen at weeks 4, 12, 26, 52, 78, and every 26 weeks thereafter. An EoS follow-up visit will take place 2 weeks after end of treatment visit. Safety evaluation telephone calls will be performed at weeks 18, 38, and every 26 weeks thereafter. The alternating safety visits and telephone contacts (TCs) result in a safety assessment frequency of approximately every 3 months throughout the entire study duration. The safety TCs must be conducted by the study investigator. During these phone calls, inquiries about adverse events, concomitant medication (including changes in use of benzodiazepines and antidepressants), changes in use of alcohol and illicit drugs, C-SSRS, and an abbreviated PBA-s (a subset of PBA-s questions on depressed mood, suicidal ideation, anxiety, irritability, loss of motivation, and obsessive-compulsive behaviors) will be conducted.

During the TCs, if the patient receives a score of 0 on the C-SSRS and PBA-s suicidal ideation assessments, the subsequent safety TCs will remain as scheduled as long as the scores of 0 are unchanged. If the patient receives a score of 1 or 2 on the C-SSRS or PBA-s suicidal ideation assessments, the safety TCs will be conducted every 4 weeks to monitor the patient's status until the scores change to 0 (after which the frequency of safety TCs will revert back as scheduled, as described above). Patients with a C-SSRS ideation score of 3 and above or a PBA-s suicidality

score of 3 and above, and all patients with C-SSRS suicidal attempts or acts (behavior), will be discontinued from treatment with study medication and will be referred to a psychiatrist for further evaluation and assessment, and handled as described in Section 6.1.5. of the protocol.

For patients with a C-SSRS or PBA-s score of 1 or 2, if in the judgment of the investigator, the patient is not in good mental health during an in-clinic visit or safety TC, the frequency and the methods for monitoring may be changed (ie, more frequent visits or TCs may be added as deemed necessary, or the patient can be referred to a psychiatrist for additional evaluation and treatment and will be monitored until recovery or their condition stabilizes, in accordance with the instructions provided in Section 6.1.5 and Section 7.8.1 of the protocol.

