Patients who discontinue study medication due to safety or tolerability reasons may continue in the study off drug and perform the scheduled visits and assessments.

[figure not shown]
Patients who withdraw from the study will have the early termination procedures and assessments performed at their final visit.

An independent internal safety committee will oversee the study (see Section 3.6.1 of the protocol).

Digital Health Sub-study (optional participation):

Motor symptoms can be objectively assessed in HD patients using different quantitative motor assessments.

Objective motor assessments aim at improving the limited sensitivity observed with categorical clinical rating scales, and reducing the intra- and inter-rater variability, as well as potential placebo effect observed in scales such as the UHDRS. Improved sensitivity for early-stage clinical studies of efficacy of a new drug on motor dysfunction is expected with objective assessments and may support early go/no go decisions in smaller cohorts of patients.

Study procedures and assessments are outlined in Table 1 of the sub-study protocol.

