9. STATISTICAL SOFTWARE

All data listings, summaries, and statistical analyses will be generated using SAS[®] version 9.4 or later.

**10. CHANGES TO ANALYSES SPECIFIED IN THE STUDY
PROTOCOL**

There are no changes to analyses specified in the study protocol.

**APPENDIX A. MODIFIED PHYSICAL PERFORMANCE TEST (MPPT)
SCORING METHOD**

| No. | Task | Items Score Values |
|-----|--|---|
| 1. | Balance Tasks | 
Standing Balance Feet Together
 
 • ≥ 10 sec = 1 • 0 - <10 sec or Unable = 0 
Standing Balance Semi Tandem
 
 • ≥ 10 sec = 1 • 0 - <10 sec or Unable = 0 
Standing Balance Tandem
 
 • ≥ 10 sec = 2 • 3 - <10 sec = 1 • 0 - <3 sec or Unable = 0 |
| 2. | Chair rise | 
 • >0 - 11 sec = 4 • >11 - 14 sec = 3 • >14 - 17 sec = 2 • >17 sec = 1 • 0, Unable = 0 |
| 3. | Lift a book and put it on a shelf | 
 • >0 - 2 sec = 4 • >2 - 4 sec = 3 • >4 - 6 sec = 2 • >6 sec = 1 • 0, Unable = 0 |
| 4. | Put on and remove a jacket (sum of time to put and to remove the jacket) | 
 • >0 - 10 sec = 4 • >10 - 15 sec = 3 • >15 - 20 sec = 2 • >20 sec = 1 • 0, Unable = 0 |
| 5. | Pick up a penny from floor | 
 • >0 - 2 sec = 4 • >2 - 4 sec = 3 • >4 - 6 sec = 2 • > 6 sec = 1 • 0, Unable = 0 |
| 6. | Turn 360 degrees | 
Steps
 
 • Continuous = 2 • Discontinuous = 0 
Steadiness
 
 • Steady = 2 • Unsteady (grabs, staggers) = 0 |
| 7. | 50-foot walk test | 
 • >0 - 15 sec = 4 • >15 - 20 sec = 3 • >20 - 25 sec = 2 • >25 sec = 1 • 0, Unable = 0 |

Statistical Analysis Plan

| | | |
|-------------------------|---|---|
| 8. | Climb one flight of stairs | 
 • >0 - 5 sec = 4 • >5 - 10 sec = 3 • >10 – 15 sec = 2 • >15 sec = 1 • 0, Unable = 0 |
| 9. | Climb 4 flights of stairs (Number of flights climbed up and down) | 
 • 4 flights = 4 • 3 flights = 3 • 2 flights = 2 • 1 flights = 1 • Unable = 0 |
| Total mPPT Score | | Sum of all Item score values [0-36] |

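### SAP 7.7 counts medicines first taken after the last dose as concomitant with pridopidine, although the supplied protocol's analysis definition covers only time on study drug, and the SAP declares no change

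*SAP*

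**What the plan says.** Both documents name concomitant medication usage as a safety endpoint (Protocol 2.3.1.1, SAP 1.2.1). They give different windows for analysing it.

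- Protocol 9.7.2, repeated in the synopsis: "Concomitant medications will include all medications taken while the patient is treated with study drug".
- SAP 7.7: medicines and therapies "from the first day of study drug administration up to the end of study as defined in the study protocol". Patients are counted once per therapeutic class and once per preferred term. With the prior-medication summary in SAP 5.5, this makes two categories, prior and concomitant. There is no post-treatment category.

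The SAP introduction settles which text is applied: "When differences exist in descriptions or explanations provided in the study protocol and this SAP, the SAP prevails". It adds that such differences will be explained in the clinical study report. SAP Section 10 then states: "There are no changes to analyses specified in the study protocol".

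Three features of the design create time in the study without drug. The SAP schedules a follow-up visit after treatment ("An EoS follow-up visit will take place 2 weeks after end of treatment visit"). Patients who stop for safety or tolerability reasons "may continue in the study off drug and perform the scheduled visits and assessments". SAP 2.1 also allows patients who completed their study period and stopped pridopidine to be screened again and re-enter.

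**The concern.** A reader takes a table of concomitant medicines to show what was given alongside the study drug. Under SAP 7.7 it also shows medicines first given after the study drug had ended, and nothing in the planned output tells the two apart.

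The medicines concerned may not be a random selection. Protocol 5.3 says: "Disallowed CYP2D6 substrates can be administered only 1 week after the discontinuation of pridopidine". A patient who observes that washout and then starts such a medicine would still be shown as taking it concomitantly with pridopidine. Patients taken off drug for suicidality are referred for psychiatric evaluation (Protocol 6.1.5, 7.1.7 and 7.8.1), so new psychotropic prescriptions after stopping are foreseeable. Apparent co-exposure would then be inflated among patients who stopped for safety reasons.

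**Working it through.** The plan states no figure to reproduce. The check compares the texts and then works out when the two windows differ.

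**1. Treatment of a medicine under each definition**

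| Medicine | Protocol 9.7.2 | SAP 7.7 |
|---|---|---|
| Ongoing at first dose, continued on drug | counted | counted |
| Started on drug, continued after last dose | counted | counted once |
| First taken after last dose, class and term both new for the patient | not counted | counted in class and term |
| First taken after last dose, new term in a class already used on drug | not counted | counted in term only; class unchanged |

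The definitions part only in the last two rows.

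**2. Which definition would be programmed.** The SAP prevails, so the wider one would be. SAP Section 10 reports no changes, so it does not alert the author of the clinical study report that this difference needs explaining.

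**3. How much off-drug time falls in the SAP window.** Protocol 3.9 gives 104 weeks of treatment and an end-of-study visit at Week 106. Ignoring visit windows, off-drug weeks = 106 − week of last dose. The early stop weeks are assumed for illustration.

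| Last dose | Off-drug weeks | Share of 106 weeks |
|---|---|---|
| Week 104 (completer) | 106 − 104 = 2 | 2/106 = 1.9% |
| Week 52, stays in study | 106 − 52 = 54 | 54/106 = 50.9% |
| Week 26, stays in study | 106 − 26 = 80 | 80/106 = 75.5% |
| Week 12, stays in study | 106 − 12 = 94 | 94/106 = 88.7% |

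These are shares of follow-up time. They are the opportunity for misclassification, not a proportion of medicines. The SAP describes a schedule that continues every 26 weeks after Week 78, so the figures apply only to the supplied protocol's 106-week schedule.

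**4. Re-entry.** SAP 2.1 has returning patients repeat screening, baseline and titration after an end-of-study visit. SAP 7.7 refers to a single first day of study drug and a single end of study, so it does not exclude medicines taken in the gap.

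**5. The right-hand limit.** SAP 7.7 relies on the protocol's definition of the end of study. Protocol 3.9 points to Section 12.4, which covers only how the end of the whole study is declared to authorities. The window therefore has no explicit end date for an individual patient.

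**6. How many entries change.** That would need the number of patients with off-drug follow-up and the number of new classes or terms they start in it. The documents give neither, so the number cannot be computed.

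**The case against.** The strongest reply is that SAP 7.7 follows the endpoint. Both documents word the endpoint as usage over the whole study, and Protocol 5.3 records medicines to the end of the study period. This stands as a reason to collect and report off-drug use. It does not replace the explicit analysis definition in Protocol 9.7.2 and the synopsis, and separate tabulation meets both.

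A second reply is that the SAP appears to follow a later protocol version. It plans up to 650 patients where the supplied protocol has up to 300, allows re-entry, and has an internal safety committee in place of the data and safety monitoring board. A reader might infer that the SAP departs, undeclared, from its own governing protocol. The documents do not support going that far, because a later version could have changed Section 9.7.2. The conflict shown is with the protocol supplied. Protocol Section 9 also lets the SAP change and detail analyses, but expects the SAP to describe the changes.

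A reader might also infer that the table would overstate non-adherence to the prohibited-medication rules. That does not follow. The lists in Protocol 5.3.2 apply during the study, not only during treatment, and the explicit 1-week allowance covers disallowed CYP2D6 substrates only. Use of prohibited medication is a protocol violation (Protocol 11.1.2), and SAP 5.7 summarizes violations from their own case report form. The medication table is not the measure of adherence.

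Finally, a split at the last dose places medicines begun in the first off-drug days under post-treatment, although the protocol uses a 1-week washout for enzyme recovery. This is a fair point about labelling. It is met if the post-treatment table keeps the time from last dose visible.

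**Conclusion.** The point holds as an inconsistency with a limited effect. Under SAP 7.7, medicines first taken after the last dose would be reported as concomitant with pridopidine, contrary to the supplied protocol's definition and without a declared change. The effect is confined to one descriptive safety table, and no inferential result depends on it.

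Its size is unknown. A reader might take the 88.7% for a Week 12 stop as the share of prescriptions misclassified. The once-per-patient counting rule rules that out, because a medicine carried over from treatment adds nothing. For completers the extra window is about 2 weeks; for patients who stop and stay it can be most of their follow-up.

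The conclusion assumes that the supplied Section 9.7.2 still applies and that SAP 7.7 is programmed as written.

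**What to change.** In SAP 7.7, define a concomitant medicine or therapy as one taken on at least one day from the first to the last dose of study drug, applied within each treatment period for re-entered patients. Tabulate those first taken after the last dose separately as post-treatment, showing time since last dose if the washout week is of interest. A medicine first taken in the gap before re-entry and continued into the second period would then count as concomitant with that period. This meets the Section 9.7.2 definition and still reports use over the whole study.

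If the single wide window is preferred, declare it in SAP Section 10 and label the table as including off-drug use.

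The cost is a short addition to SAP 7.7 and one extra table or column. Protocol 5.3 already has start and end dates of medicines entered on the case report form, so no new data are needed.

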7.8. Other Safety Assessments

Summary statistics for the C-SSRS baseline version will be presented at screening. Patients with suicidal ideation and behavior items will be summarized as categorical data using descriptive statistics.

Summary statistics for the C-SSRS last visit version will be presented at overall postbaseline. Patients with suicidal ideation and behavior items will be summarized as categorical data using descriptive statistics.

8. TOLERABILITY VARIABLES AND ANALYSIS

Tolerance is summarized with the safety analysis.

9. STATISTICAL SOFTWARE

All data listings, summaries, and statistical analyses will be generated using SAS[®] version 9.4 or later.

**10. CHANGES TO ANALYSES SPECIFIED IN THE STUDY
PROTOCOL**

There are no changes to analyses specified in the study protocol.

**APPENDIX A. MODIFIED PHYSICAL PERFORMANCE TEST (MPPT)
SCORING METHOD**

| No. | Task | Items Score Values |
|-----|--|---|
| 1. | Balance Tasks | 
Standing Balance Feet Together
 
 • ≥ 10 sec = 1 • 0 - <10 sec or Unable = 0 
Standing Balance Semi Tandem
 
 • ≥ 10 sec = 1 • 0 - <10 sec or Unable = 0 
Standing Balance Tandem
 
 • ≥ 10 sec = 2 • 3 - <10 sec = 1 • 0 - <3 sec or Unable = 0 |
| 2. | Chair rise | 
 • >0 - 11 sec = 4 • >11 - 14 sec = 3 • >14 - 17 sec = 2 • >17 sec = 1 • 0, Unable = 0 |
| 3. | Lift a book and put it on a shelf | 
 • >0 - 2 sec = 4 • >2 - 4 sec = 3 • >4 - 6 sec = 2 • >6 sec = 1 • 0, Unable = 0 |
| 4. | Put on and remove a jacket (sum of time to put and to remove the jacket) | 
 • >0 - 10 sec = 4 • >10 - 15 sec = 3 • >15 - 20 sec = 2 • >20 sec = 1 • 0, Unable = 0 |
| 5. | Pick up a penny from floor | 
 • >0 - 2 sec = 4 • >2 - 4 sec = 3 • >4 - 6 sec = 2 • > 6 sec = 1 • 0, Unable = 0 |
| 6. | Turn 360 degrees | 
Steps
 
 • Continuous = 2 • Discontinuous = 0 
Steadiness
 
 • Steady = 2 • Unsteady (grabs, staggers) = 0 |
| 7. | 50-foot walk test | 
 • >0 - 15 sec = 4 • >15 - 20 sec = 3 • >20 - 25 sec = 2 • >25 sec = 1 • 0, Unable = 0 |

Statistical Analysis Plan

| | | |
|-------------------------|---|---|
| 8. | Climb one flight of stairs | 
 • >0 - 5 sec = 4 • >5 - 10 sec = 3 • >10 – 15 sec = 2 • >15 sec = 1 • 0, Unable = 0 |
| 9. | Climb 4 flights of stairs (Number of flights climbed up and down) | 
 • 4 flights = 4 • 3 flights = 3 • 2 flights = 2 • 1 flights = 1 • Unable = 0 |
| Total mPPT Score | | Sum of all Item score values [0-36] |
